#### 8.9.4 Imaging Assessments

All baseline evaluations will be performed as closely as possible to the beginning of treatment ( $\leq 35$  days). For subsequent evaluations, the method of assessment and techniques will be the same as those used at baseline.

To assess the antitumor effect of a treatment, imaging-based evaluation is preferable to evaluation by clinical examination. CT and MRI should be performed using contiguous slices of 10 mm or less. Spiral CT should be performed using a 5-mm contiguous reconstruction algorithm (interval). If a 5-mm contiguous reconstruction algorithm (interval) is not used, as a general rule, the lesion diameter should be no less than double the reconstruction algorithm (interval) and must be at least 20 mm for nonspiral CT or at least 10 mm for spiral CT. (If available, spiral CT is preferred in all instances.) This applies to tumors of the chest, abdomen, and pelvis. Head and neck tumors and those of the extremities typically require specific protocols. Sodium Fluoride PET-CT +/- IV contrast may be used as an alternative to CT/bone scan if available. Brain MRI should be ordered as per standard of care practice in symptomatic or small cell carcinoma patients.

#### 8.9.5 PSA

PSA testing should be performed at each cycle (every 4 weeks). To report PSA-based outcomes, PCWG3 recommends that the percent of change in PSA from baseline to 8 and 12 weeks depending on trial design (or earlier for those who discontinue therapy) and the maximum decline in PSA that occurs at any point after treatment be reported for each patient using a waterfall plot.

### **8.9.6 Non-PSA Tumor markers (Standard of care)**

Chromogranin-A levels will be measured at baseline and on day 1 of each cycle if elevated. CEA should be assessed at baseline and if elevated, followed on day 1 of each cycle.

### **8.9.7 Measurable disease**

According to iRECIST, measurable disease is defined as at least 1 lesion  $\geq 10$  mm in its longest diameter as measured with computerized tomography (CT) with slice thickness no greater than 5 mm;  $\geq 10$  mm as measured with calipers on clinical exam; or  $>15$  mm for nodal metastases using the shortest diameter. All tumor measurements will be taken using a ruler or calipers and recorded in millimeters (or decimal fractions of centimeters). In the case of skin lesions, documentation by color photography, including a ruler to estimate the size of the lesion, is recommended.

Only tumor lesions that have not been previously irradiated will be considered measurable.

### **8.9.8 Nonmeasurable disease**

Following iRECIST, all other lesions (or sites of disease) will be considered nonmeasurable disease. This includes small lesions (longest diameter  $< 20$  mm with conventional techniques or  $< 10$  mm using spiral CT scan) and any of the following:

- bone lesions
- ascites
- pleural or pericardial effusion
- lymphangitis cutis or pulmonis
- abdominal masses that are not confirmed and followed by imaging techniques
- cystic lesions
- lesions occurring within a previously irradiated area unless they are documented as new lesions since the completion of radiation therapy

### **8.9.9 Target (nodal and visceral) lesions**

Following iRECIST, progression in a nodal or visceral site (i.e., liver and lung) is sufficient to document disease progression. The presence or absence of nodal and visceral disease before and after treatment should be recorded separately.

All measurable lesions (up to a maximum of 5 lesions per organ and 10 lesions in total) will be identified as target lesions to be measured and recorded at baseline. The target lesions should be representative of all involved organs. Target lesions will be selected on the basis of size (i.e., the largest area) and suitability for accurate, repeated measurements (either by imaging techniques or clinically). The sum of the longest diameter (LD) of all target lesions will be calculated and reported as the baseline sum LD. The baseline sum LD will be used as a reference by which to characterize the objective tumor response.

Because small lymph nodes are difficult to measure accurately and may not be malignant, a lymph node must measure at least 1.5 cm by short axis by spiral CT to be considered a target lesion.

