### 8.9.12 New lesions

The appearance of up to 10 new measurable lesions should be recorded. Each new lesion should be reassessed using the same imaging modality at each time point. If measurable, the LD of each new lesion (including lymph nodes) should be recorded in the CRF and the sum LD of new and old lesions should be calculated. See Table 1 for a description of the determination of progression based on the presence of new lesions.

**Note:** The appearance of a new lesion does not by itself satisfy the criteria for confirmed progressive disease. Rather, the tumor burden imposed by the new lesions must be evaluated within the context of the total tumor burden (i.e., preexisting plus new lesions). Confirming progression in target lesions, nontarget (i.e., other than bone) lesions, and bone lesions requires 2 assessment time points. The first must occur at Week 8 (or later) and the second occurring at least 6 weeks after the first. Progression declared at the first time point remains unconfirmed unless assessments at the second time point demonstrate continuing or worsening progression as described in section 8.10.

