### 8.10.1 Measurable soft-tissue lesions

When evaluating soft-tissue lesions, the definitions in Table 1 apply.

Response	Evaluation of Soft-Tissue Lesions
Complete response (CR)	the disappearance of clinical and radiological evidence of all target lesions and normalization of tumor marker levels
Partial response (PR)	a decrease from baseline $\geq 30\%$ in the sum of the LD of all target lesions
Progressive disease (PD)	an increase $\geq 20\%$ in the sum of the LD of all target lesions based on the smallest sum LD since treatment started or the appearance of one or more new lesions or the appearance of new lesions
Stable disease (SD)	neither sufficient shrinkage to qualify for PR nor sufficient increase to qualify for PD based on the smallest sum LD recorded since treatment started

In some circumstances, it may be difficult to distinguish residual disease from normal tissue. When the evaluation of complete response depends on this determination, it is recommended that the residual lesion be investigated (e.g., fine needle aspirate or biopsy) before confirming the complete response status.

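### Nodal targets qualify by short axis but are followed by longest diameter, so nodal response or progression can be misclassified in either direction

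*Combined protocol and SAP*

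**What the plan says.** **Entry.** Under Section 8.9.7 a node is measurable when it exceeds 15 "mm for nodal metastases using the shortest diameter". Section 8.9.9 adds that "a lymph node must measure at least 1.5 cm by short axis by spiral CT to be considered a target lesion", on the ground that small nodes are hard to measure and might be benign.

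**Scoring.** Section 8.9.9, whose heading covers both nodal and visceral lesions, then says: "The sum of the longest diameter (LD) of all target lesions will be calculated and reported as the baseline sum LD". It continues: "The baseline sum LD will be used as a reference by which to characterize the objective tumor response". For new lesions, Section 8.9.12 is explicit: "If measurable, the LD of each new lesion (including lymph nodes) should be recorded in the CRF". Table 1 in Section 8.10.1 sets PR at a fall of at least 30%, and PD at a rise of at least 20%, "in the sum of the LD of all target lesions"; SD is whatever lies between. CR requires "the disappearance of clinical and radiological evidence of all target lesions and normalization of tumor marker levels".

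No section scores a target node by short axis after entry. None gives a nodal size that counts as resolved.

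**Use.** Section 11.5.1 counts CR and PR as response, so SD is a non-response. Section 8.10.6 also introduces Table 4 for immune-modified response, with other limits (a fall of at least 50%, or a rise of at least 25%, in total measurable burden). Section 8.11.3 uses Table 4 for the immune-modified PFS.

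**The concern.** The short axis decides whether a node is disease at all, and the longest diameter decides whether that disease has responded or progressed. The two need not move together. A node that thins while staying long can look stable on the scored dimension although it has dropped below the size that qualified it. A node that thickens without lengthening can look stable while it grows on the qualifying dimension.

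Nodes are relevant here. Section 3.1 lists bulky lymphadenopathy among the features of this disease, and nodes of 2 cm or more in short axis are one of the routes into eligibility Criterion 2. The decision limits are small counts: 2 responses in 18 to continue, 5 in 44 to declare activity. A few reclassified men could change the result. Best overall response is the investigator's determination (Section 8.10.6), and stage 2 adds 2-3 sites (Section 11.9), so the rule has to be one that every reader applies alike.

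**Working it through.** **1. Plan's own figures.** Inputs from Section 11.1: 18 men in stage 1, stop at 1 or fewer responses; 26 more; success at 5 or more of 44; p0 = 5%, p1 = 20%. With X1 ~ Bin(18, p) and X2 ~ Bin(26, p):

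P(success) = sum over x = 2 to 18 of P(X1 = x) · P(X2 ≥ 5 − x); P(stop early) = P(X1 ≤ 1).

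Results: early stopping at 5% is 0.7735 (stated 0.77), type I error 0.0495 (stated 0.05), power at 20% is 0.8806 (stated 88%). The design figures are sound; the issue is the response definition.

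**2. Node-only patients.** Sizes are assumed, since the documents give none. LD is longest diameter and SA short axis, in mm.

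| Change (LD x SA) | LD change | Table 1 as written | SA change | Same limits on SA |
|---|---|---|---|---|
| 28 x 18 to 21 x 9 | (28−21)/28 = −25% | SD | (18−9)/18 = −50% | PR-sized |
| 25 x 16 to 18 x 10 | (25−18)/25 = −28% | SD | (16−10)/16 = −37.5% | PR-sized |
| 28 x 18 to 30 x 24 | (30−28)/28 = +7% | SD | (24−18)/18 = +33% | PD-sized |
| 20 x 15 to 12 x 9 | (20−12)/20 = −40% | PR | (15−9)/15 = −40% | PR-sized |

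In general a node-only patient stays non-PR while LD remains above 70% of baseline, whatever the short axis does. The last row shows the limit of the point: equal proportional shrinkage gives the same category. The error reverses when LD falls proportionally more than the short axis.

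**3. Nodal plus visceral targets (assumed sizes).** Node 30 x 20 to 22 x 9, visceral lesion 20 to 16.
- All LD: 30 + 20 = 50 to 22 + 16 = 38, −24.0%, SD.
- SA for the node: 20 + 20 = 40 to 9 + 16 = 25, −37.5%, PR.

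Now let the same node halve on both axes while the visceral lesion stays at 20.
- All LD: 50 to 15 + 20 = 35, −30.0%, PR.
- SA for the node: 40 to 10 + 20 = 30, −25.0%, SD.

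The axis also sets the weight a node carries in the sum, so with mixed targets the categories can differ even when the node shrinks evenly. In this case the LD rule is the more generous one.

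**4. Sensitivity of the primary test.** This applies only if Table 1 governs the primary ORR and only for missed responses. Let m be the share of true responses recorded as SD; the recorded rate is 0.20 · (1 − m).

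| m (assumed) | Recorded rate | Power | Chance of stopping at stage 1 |
|---|---|---|---|
| 0% | 0.20 | 0.881 | 0.099 |
| 10% | 0.18 | 0.824 | 0.139 |
| 20% | 0.16 | 0.745 | 0.192 |

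Nothing in the documents fixes m.

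**5. CR row.** A node that returns to normal size but stays visible does not meet disappearance. If its sum has fallen at least 30% the man is scored PR instead of CR. Both count in ORR, so this wording alone leaves ORR unchanged.

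**The case against.** The best defence is that the plan is consistent within its scoring rules: longest diameter is used for the baseline sum, new lesions, PR, SD and PD. Screening on one dimension and tracking another is a choice, not a contradiction. The sections cite iRECIST, RECIST 1.1 and PCWG3, but the protocol does not reproduce how those sources sum nodes, so departure from them cannot be shown from the documents. That stands. What remains is that the plan gives its reason for judging nodes by short axis, then drops that dimension without explanation.

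Several stronger readings are tempting and go too far:

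- *The primary ORR loses nodal responders.* Section 8.10.6 says immune-modified responses will be described with Table 4, so it is unclear that Table 1 governs the immune-based primary endpoint. Any effect there is conditional.
- *Power falls to 0.82 or 0.74.* No nodal or node-dominant share is given, and errors run both ways. Missed responses alone would be conservative and would not inflate type I error.
- *The CR wording lowers ORR.* It moves men from CR to PR only. Section 8.10.1 also recommends sampling a residual lesion that is hard to tell from normal tissue, so CR with visible residual tissue is not wholly excluded.
- *The trial selects men by nodal size.* Nodes are one branch of one of three alternatives in Criterion 2; Criterion 1 needs none, and Section 3.1 also names predominant visceral spread.
- *The two qualifying limits conflict in substance.* More than 15 mm and at least 1.5 cm differ only for a node of exactly 15 mm, which is editorial.

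**Conclusion.** The point holds in a bounded form and should be corrected. As written, nodal targets enter by short axis and are followed by longest diameter, and plausible shape changes cross the 30% or 20% limit on one axis but not the other. The RECIST 1.1 response rate and the rPFS based on it are exposed. The primary ORR is exposed where Table 1 governs, and the documents need to say whether it does.

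The size is unknown. The examples rest on assumed measurements, and the power range of 0.88 to 0.74 rests on an assumed 0% to 20% of true responses being missed with no offsetting errors. A reader might infer that the primary result is biased downward by a known amount; the documents support neither the direction nor the amount. The CR wording is a separate, smaller matter that affects the CR count and not ORR.

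**What to change.** 1. In Sections 8.9.9 and 8.9.12 and in Table 1, define the sum as longest diameter for non-nodal targets plus short axis for nodal targets, at baseline and at every follow-up.
2. In the CR row, state a pre-specified short-axis limit, taken from the cited criteria, below which a nodal target counts as resolved.
3. Use one qualifying limit in Sections 8.9.7 and 8.9.9.
4. State whether Table 1 or Table 4 defines the immune-based primary response.

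**Cost.** Protocol wording and a CRF field. No extra scans are needed, but the short axis is currently required only for qualification, so recording it at each follow-up is added reading work.

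**Safeguard.** In an open-label single-arm trial, re-scoring after outcomes are known can introduce bias. Scans already read should be re-measured from stored images under a rule fixed beforehand, for all patients, by readers unaware of the recorded response where existing staff allow. Report the ORR based on longest diameter alongside as a sensitivity analysis.

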### 8.9.10 Bone lesions

When the bone scan is the sole indicator of progression at baseline, disease progression in bone is defined as 2 or more new lesions seen on bone scan compared with a prior scan used for trial entry. In situations where scan findings suggest a flare reaction or where new lesion(s) may represent trauma, confirm these results with other imaging modalities (e.g., MRI or fine-cut CT). If many new areas of uptake are observed, confirmation is generally not necessary.

### 8.9.11 Nontarget lesions

All other lesions (or sites of disease) will be identified as nontarget lesions and recorded at baseline. Nontarget lesions will include measurable lesions that exceed the maximum number per organ (5) or total of all involved organs (10), as well as nonmeasurable lesions. The presence or absence of these lesions will be recorded on the CRF and should be evaluated at the same assessment time points as all target lesions.

### 8.9.12 New lesions

The appearance of up to 10 new measurable lesions should be recorded. Each new lesion should be reassessed using the same imaging modality at each time point. If measurable, the LD of each new lesion (including lymph nodes) should be recorded in the CRF and the sum LD of new and old lesions should be calculated. See Table 1 for a description of the determination of progression based on the presence of new lesions.

**Note:** The appearance of a new lesion does not by itself satisfy the criteria for confirmed progressive disease. Rather, the tumor burden imposed by the new lesions must be evaluated within the context of the total tumor burden (i.e., preexisting plus new lesions). Confirming progression in target lesions, nontarget (i.e., other than bone) lesions, and bone lesions requires 2 assessment time points. The first must occur at Week 8 (or later) and the second occurring at least 6 weeks after the first. Progression declared at the first time point remains unconfirmed unless assessments at the second time point demonstrate continuing or worsening progression as described in section 8.10.

## 8.10 Response Criteria

Response and progression will be evaluated in this study using a modified PCWG3 where RECIST 1.1 is replaced with iRECIST criteria and the guidelines for prostate cancer endpoints developed by the Prostate Cancer Clinical Trials Working Group (PCWG3). In brief, iRECIST defines an immune unconfirmed progressive disease (UPD) on the basis of RECIST 1.1 principles and now requires confirmation of progression. Confirmation is done by observing either a further increase in size or number of new lesions identified (target, non-target) or progression by RECIST 1.1. However if progression is not confirmed but instead shrinkage occurs, compared to baseline, which meets RECIST 1.1 criteria of complete response, partial response, or stable disease; then the bar is reset so that UPD needs to occur again, compared with nadir values, and then be confirmed again.

Trial objectives are defined based on controlling, relieving, or eliminating disease manifestations that are present when treatment is initiated, or preventing or delaying the development of disease manifestations that are expected to occur (or in some cases both). Traditional measures of response reflect when a treatment is working and measures of progression indicate when a drug should be stopped. Because assessing response in bone (the most common site of prostate cancer spread) is uncertain and the clinical significance of PSA changes in response to therapy is not a reliable predictor of response, measures of response have been expanded in consortium trials to include measures of progression.

Subjects will need to be reevaluated for response every 2 cycles (or more frequently if indicated), according to the guidelines below.

### 8.10.1 Measurable soft-tissue lesions

When evaluating soft-tissue lesions, the definitions in Table 1 apply.

Response	Evaluation of Soft-Tissue Lesions
Complete response (CR)	the disappearance of clinical and radiological evidence of all target lesions and normalization of tumor marker levels
Partial response (PR)	a decrease from baseline $\geq 30\%$ in the sum of the LD of all target lesions
Progressive disease (PD)	an increase $\geq 20\%$ in the sum of the LD of all target lesions based on the smallest sum LD since treatment started or the appearance of one or more new lesions or the appearance of new lesions
Stable disease (SD)	neither sufficient shrinkage to qualify for PR nor sufficient increase to qualify for PD based on the smallest sum LD recorded since treatment started

In some circumstances, it may be difficult to distinguish residual disease from normal tissue. When the evaluation of complete response depends on this determination, it is recommended that the residual lesion be investigated (e.g., fine needle aspirate or biopsy) before confirming the complete response status.

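### Target-lesion progression in Table 1 is a 20% rise from nadir with no minimum increase in millimetres, so in small sums reading error alone can produce progression, mainly affecting rPFS and response duration

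*Combined protocol and SAP*

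**What the plan says.** Section 8.10.1 states that Table 1 governs soft-tissue lesions. Apart from new lesions, Table 1 calls progressive disease when there is a rise of at least 20% "in the sum of the LD of all target lesions based on the smallest sum LD" since treatment began. Neither Table 1 nor any other section adds an absolute minimum for target lesions.

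The entry limits allow small sums. Section 8.9.7 needs only one lesion of at least 10 "mm in its longest diameter as measured with computerized tomography (CT) with slice thickness no greater than 5 mm". For nodes, section 8.9.9 says that "a lymph node must measure at least 1.5 cm by short axis by spiral CT to be considered a target lesion".

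Progression has a confirmation step. Section 8.9.12 asks for a first assessment at week 8 or later and a second at least 6 weeks after it: "Progression declared at the first time point remains unconfirmed unless assessments at the second time point demonstrate continuing or worsening progression". Section 8.10 likewise asks for confirmation under iRECIST and resets the process if progression is not confirmed. Neither section sets a millimetre minimum at the second assessment.

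For PSA, section 8.10.2 does pair a relative with an absolute condition: at least 25% and at least 2.0 ng/mL over the nadir.

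Table 4, which section 8.11.3 uses for the immune-modified PFS estimate, is on a different scale: a 25% rise in tumor volume or burden relative to nadir.

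**The concern.** A purely relative threshold shrinks with the sum, while reading error in millimetres need not. The reference is also the smallest of several readings, so one reading that is too low lowers the bar for every later scan. Small sums are therefore the most likely to be called progressive by chance. They occur in men who enter with little measurable disease and in men who have responded: a 30% fall takes any baseline sum under 25/0.70 = 35.7 mm to a nadir below 25 mm.

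Under Table 3 (section 8.10.6), target-lesion progression makes the overall response progressive. It ends response duration (section 8.11.2) and counts as a PFS event (section 8.11.3). It also closes the window for best overall response (section 8.10.6). The PSA rule shows that the authors guarded low values against this problem elsewhere, so the gap in Table 1 looks like an omission.

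**Working it through.** **The plan's own figures.** The plan gives no reading error and no false-progression rate. Its calculated figures are for the two-stage design (18 then 26 men, stop at 1 or fewer, promising at 5 or more of 44). The exact two-stage binomial gives power 0.8806, one-sided type I error 0.0495 and early-termination probability 0.7735, against the stated 88%, 0.05 and 0.77. Nothing below alters these.

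**Step 1: size of the qualifying rise.** Rise needed = 0.20 × nadir sum.

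| Nadir sum (mm) | Rise needed now (mm) | Rise needed with a 5 mm minimum (mm) |
|---|---|---|
| 7 (10 mm after a 30% fall) | 1.4 | 5 |
| 10 (smallest single non-nodal target) | 2.0 | 5 |
| 15 (smallest single nodal target) | 3.0 | 5 |
| 20 | 4.0 | 5 |
| 25 | 5.0 | 5 |
| 30 | 6.0 | 6 |

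The two rules meet at 5/0.20 = 25 mm. From there up the minimum changes nothing.

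**Step 2: chance of crossing with no true change.** Assumptions: constant true sum S, independent normal reading error on the sum with SD σ, a baseline and three follow-up scans 8 weeks apart, and nadir = running minimum including baseline. The values of σ are assumed.

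The first follow-up scan has a closed form. A call needs X1 − 1.2·X0 ≥ 0, which has mean −0.2S and variance 2.44σ². The chance is therefore the upper normal tail beyond 0.2S/(1.562σ). For S = 10 mm:
- σ = 0.5: z = 2/0.781 = 2.56, chance 0.5%
- σ = 1.0: z = 2/1.562 = 1.28, chance 10%
- σ = 1.5: z = 2/2.343 = 0.85, chance 20%
- σ = 2.0: z = 2/3.124 = 0.64, chance 26%

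Over three scans, by simulation:

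| Sum | σ (mm) | At least once, 20% only | Two consecutive scans, 20% only | At least once, 20% and 5 mm | Two consecutive scans, 20% and 5 mm |
|---|---|---|---|---|---|
| 10 mm | 0.5 | 3% | 0.2% | 0% | 0% |
| 10 mm | 1.0 | 37% | 9% | 0.1% | about 0% |
| 10 mm | 1.5 | 61% | 21% | 5% | 0.3% |
| 10 mm | 2.0 | 72% | 29% | 17% | 2% |
| 20 mm | 0.5 | 0% | 0% | 0% | 0% |
| 20 mm | 1.0 | 3% | 0.2% | 0.1% | about 0% |
| 20 mm | 1.5 | 19% | 3% | 5% | 0.3% |
| 20 mm | 2.0 | 37% | 9% | 17% | 2% |

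For a 30 mm sum the two-scan figure without a minimum is 0% to 2% over the same range of σ.

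**Step 3: what the two-scan column stands for.** Consecutive scans 8 weeks apart meet the 6-week minimum of section 8.9.12, and the column follows that section's looser wording, under which the rise need only persist. If confirmation is taken to require a further increase in size, as section 8.10 also puts it, the true figures would be lower.

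**The case against.** The strongest reply is confirmation. A reader might take the 37% to 72% figures as the false-progression rate of the trial's main endpoint. They are not: they count any single crossing, and sections 8.9.12, 8.10 and 8.10.6 leave a single crossing unconfirmed. Confirmation cuts the 10 mm figures to 9% to 29% for SDs of 1.0 to 2.0 mm. It does not remove the problem, because the second scan has no millimetre minimum either and a nadir read too low carries forward to it.

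A reader might also infer that the decision at 5 of 44 responders could turn on this. The documents do not support that. The primary endpoint is iRECIST-based, an unconfirmed progression can be followed by a response, and treatment past radiologic progression is permitted, so later responses can be seen. To lose a response, a man would need a small sum, a false progression that is confirmed, and only then a first true response. The plan gives no distribution of baseline sums from which to count such men.

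A third tempting reading sets a 10 mm target beside the 10 mm slices that section 8.9.4 allows. That section also says that, without the 5 mm reconstruction, a lesion should be at least double the interval and "must be at least 20 mm for nonspiral CT or at least 10 mm for spiral CT", and section 8.9.8 treats lesions under 20 mm by conventional techniques as nonmeasurable. A 10 mm target on 10 mm slices is not what the protocol describes. Slice thickness is in any case only a rough marker of error in a longest diameter.

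Three further points stand. At an SD of 0.5 mm the problem nearly vanishes. Up to 10 targets are summed, so many men may exceed 25 mm, and the background describes bulky nodal disease. Section 8.10 also invokes RECIST 1.1 principles, which could be argued to bring in further conditions. The protocol states none, however, and a programmer working from Table 1 would apply 20% alone.

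**Conclusion.** The point holds as a gap in the progression definition. As written, a 2 mm rise in a 10 mm sum is progression at that scan, and the required rise is below 5 mm for every nadir sum under 25 mm. With no true change and an assumed reading SD of 0.5 to 2.0 mm, two-scan false progression over three scans runs from 0.2% to 29% at 10 mm and from 0% to 9% at 20 mm. With a 5 mm minimum it is at most about 2% at either size.

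The effect falls mainly on rPFS and response duration in men with small sums. It is largest in any RECIST 1.1 read taken without confirmation, to which the single-crossing figures would apply. An effect on the primary decision is possible but not quantified, and the share of men affected is unknown. The result rests on the assumed SDs, on independent errors and on the two-scan proxy. It should be corrected, but it does not undermine the design: sample size, power and type I error are unchanged.

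**What to change.** In Table 1, define target-lesion progression as an increase of at least 20% **and** at least 5 mm in the sum of longest diameters over the smallest sum since treatment started. The 5 mm is the slice limit already in section 8.9.7. Apply the definition to the RECIST 1.1 read and to the initial, unconfirmed progression call of the iRECIST read. State in the same place whether the RECIST 1.1 read needs confirmation.

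Do not carry the millimetre minimum into Table 4, which works on tumor volume or burden with a 25% threshold. Reconcile Table 4 with Table 1 separately, and say which one defines progression for the iRECIST-based endpoints and for the immune-modified PFS in section 8.11.3.

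The Table 1 change costs one line of text and one derivation in the response program. Reconciling Table 4 is additional work. The downside is that true progression in a very small sum may be called one scan later. The change concerns how endpoints are classified, not how patients are managed.
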